12.2 Eye Symptoms

Analysis of eye symptom-related AEs for all eye symptoms, severe eye symptoms, and serious eye symptoms will be based on new events that occurred after Screening. Severe eye symptoms are events that are assigned with grade 3 intensity or greater.

The frequency distribution of participants who experienced 1, 2, or ≥ 3 eye symptom-related AEs in one or both eyes during Day 1 to Day 15 will be summarized by treatment group for all eye symptoms, severe eye symptoms, and serious eye symptoms. The frequency and proportion (expressed in percent) of participants and 95% CI for proportions will be provided for the summary. For computing proportions, the denominator is the number of participants in the Safety population for the given treatment group.

Additionally, the frequency of symptom-related AEs and frequency and proportion (expressed in percent) of participants with eye symptom-related AEs in one or both eyes will be provided by PT and by treatment group for the following:

- All eye symptoms
- Severe eye symptoms
- Serious eye symptoms
- The frequency and proportion of participants with eye symptom-related AEs in one or both eyes that observed at Days 1, 4, 7, 10, 14, 15, Days 1-15 combined (i.e. any eye symptom-related AE observed on any Days 1-15), 28, 42, and Days 28-42 combined (i.e.

any eye symptom-related AE observed on any Days 28-42) will be provided by treatment group for the following: All eye symptoms

- Severe eye symptoms
- Serious eye symptoms

For the by-time point summary, the denominator for the proportion is the number of participants with eye symptom assessment at the given time point.

Any day that a participant reported an eye symptom-related AE in one or both eyes after screening will be counted toward the number of days of having eye symptoms in the study for that individual. Number of days of having eye symptoms will be summarized by treatment group using descriptive statistics for the following:

- All eye symptoms
- Severe eye symptoms
- Serious eye symptoms

Additionally, categorical number of days of having eye symptoms for participants with these events will be summarized by treatment group as follows:

- 1-3 days
- 4-6 days
- 7-9 days
- 10-12 days
- 13-15 days
- ≥ 16 days

The summary will include the frequency and proportion (expressed in percent) of participants for each category. For computing proportion, the denominator will be the number of participants with eye symptom-related AEs in the treatment group.

Average duration, expressed in hours, of eye symptom-related AEs in one or both eyes that were observed after screening for an individual participant will be computed as the average of duration of these events. Average duration, will be summarized by treatment group using descriptive statistics for the following:

- All eye symptoms
- Severe eye symptoms
- Serious eye symptoms

Additionally, categorical average duration of eye symptoms for participants with these events will be summarized by treatment group as follows:

- ≤ 1 hour
- $> 1-3$ hours
- $> 3-5$ hours
- $> 5-24$ hours

- >24 hours

The summary will include the frequency and proportion (expressed in percent) of participants for each category. For computing proportions, the denominator will be the number of participants with eye symptoms in the treatment group.

Exploratory safety analysis may be performed to further assess eye symptoms (all, severe, serious) reported from Day 1 through Day 15 if deemed to add value. The data may be fit in the same spirit as the efficacy model using hierarchical Bayesian nonlinear mixed-effects logistics regression model, or other simpler model-based assessments.

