3.2. Secondary Objectives and Endpoints

Table 6. Secondary Objectives and Endpoints

Objectives	Endpoints
Bactericidal activity	
Demonstrate the EBA of the first 2 days (screening [“0”] to Day 2) and of the remaining 12 days (Day 2 to Day 14) of 5 dose regimens of TBA-7371 monotherapy and HRZE, as assessed by CFU counts on solid media culture.	
 Slope, i.e. average change per day, from screening (“0”) to Day 2 [0-2] and from Day 2 to Day 14 [BA_{CFU}(2-14)] of the log CFU counts.
Demonstrate the bactericidal activity of 5 dose regimens of TBA-7371 monotherapy and of HRZE, as assessed by alternative methods: 
 time to sputum culture positivity (TTP) in (MGIT) culture LAM assay 	
 Slope of the time to sputum culture positivity (TTP) in the MGIT system from screening (“0”) to Day 14 [BA_{TTP}(0-14)], from screening to Day 2 [BA_{TTP}(0-2)], and from Day 2 to Day 14 [BA_{TTP}(2-14)]. Slope of the log concentration of sputum LAM from screening (“0”) to Day 14 [BA_{LAM}(0-14)], from screening to Day 2 [BA_{LAM}(0-2)], and from Day 2 to Day 14 [BA_{LAM}(2-14)].
Safety	
Assess the adverse event (AE) profile of each dose regimen of TBA-7371 and HRZE over the 14-day treatment period.	
 Frequency from Day 1 through Day 15 of participants with AE and frequency of AEs: overall, by body system, and preferred term; by seriousness, intensity (severity), expectedness and relatedness to study drug.
Assess the impact on eye symptoms, visual acuity and color vision of each dose regimen of TBA-7371 and HRZE over the 14-day treatment period.	
From Day 1 through Day 15:
 
 Frequency of participants with any new (vs. screening) eye symptom in one or both eyes. Mean and frequency distribution of duration of each eye symptom.

Objectives	Endpoints
	
 Mean and frequency distribution of percentage of days with any eye symptom and each of the eye symptoms. Mean/median change in visual acuity score from screening to lowest score during Days 1-15. Frequency of participants with any new color vision abnormalities (tritan, protan, deutan) in one or both eyes and degree of severity (mild, moderate, severe).

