
8.3.7. Eye Assessment

On each eye assessment day participants will undergo the following 3 eye assessment procedures (always in this order):

- i) Eye symptom assessment using the standardized script provided in Section 10.5 (Appendix 5)
- ii) Visual acuity test by means of the Rosenbaum Pocket Eye Screener on each eye.
- iii) Color vision by means of the Waggoner Computerized Color Vision Test on each eye.

The visual acuity test and Waggoner Computerized Color Vision Test (updated computerized version of the paper-based ColorDX test) will be conducted by staff members trained by an ophthalmologist. Whenever possible the same staff member should conduct all eye assessment procedures on an individual participant.

Details on use of the Rosenbaum Pocket Eye Screener and Waggoner Computerized Color Vision Test are provided in the study specific manual(s).

The 3 eye assessment procedures will be conducted on each of the eye assessment days as follows:

Screening Phase

Once in the AM.

This assessment will be used to assess eligibility (Exclusion Criteria, Section 5.2).

Study Treatment Phase

On Days 1, 4, 7, 10 and 14, 2.5 hours after the 1st daily dose of study drug (see Table 4).

Follow-up Phase

On Days 15, 28 and 42 during scheduled visit.

Early withdrawal visit

If the participant withdraws from the study between Day 1 and 14.

Regarding eye symptoms, based on the outcome of study TBA7371-001, special attention will be paid to blurred vision, photophobia, altered color vision and increased lacrimation, but any other eye symptom will be assessed if it occurs (see Section 10.5, Appendix 5).

Intensity (severity) grading of eye symptoms reported in Section 10.4 (Appendix 4, page 20) may help the investigator. However, the investigator is not obliged to follow these criteria and his/her medical judgement should prevail. The visual acuity and color vision tests will complement the clinical assessment of eye symptoms in the assessment of AE intensity and seriousness.

Any eye symptom and/or abnormal visual acuity / color vision test outcome considered clinically meaningful by the investigator must be recorded as AE.

Participants with eye symptom-related AE classified as severe (\geq Grade 3) and/or serious will contribute to the primary safety end-point (see Section 3.1, Table 5).

Participants with any eye symptom will contribute to secondary safety end-points (see Section 3.2, Table 6).

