10.2.6. Recording and Follow-up of AEs and SAEs

10.2.6.1. AE and SAE Recording

- Care will be taken not to introduce bias when detecting AE and SAE. Open-ended and non-leading verbal questioning of the participant is the preferred method to inquire about AE occurrences.
- When an AE/SAE occurs, it is the responsibility of the investigator to review all documentation (e.g., hospital progress notes, laboratory reports, and diagnostics reports) related to the event.
- The investigator will then record all relevant AE/SAE information in the CRF.
- AE will be reported on the AE CRF using a recognized medical term or diagnosis that accurately reflects the event.
- AE evaluations will be reviewed by the principal investigator or a medically qualified delegate. AE CRF pages are to be completed by members of the study team designated in writing by the principal investigator. The onset and resolution dates of an AE and action taken in response to the AE will be documented.
- After the initial AE/SAE report, the investigator is required to proactively follow each participant at subsequent visits/contacts. All SAE and non-serious AESI will be followed until resolution, stabilization, the event is otherwise explained, or the participant is lost to follow-up.
- It is **not** acceptable for the investigator to send photocopies of the participant's medical records to the sponsor in lieu of completion of the AE/SAE CRF page.
- There may be instances when copies of medical records for certain cases are requested by the medical monitor, the IDMC or the sponsor. In this case, all participant identifiers, with the exception of the participant number, will be redacted on the copies of the medical records before submission.
- The investigator will attempt to establish a diagnosis of the event based on signs, symptoms, and/or other clinical information. Whenever possible, the diagnosis (not the individual signs/symptoms) will be documented as the AE/SAE.
- SAE will be assessed for severity and causal relationship to the study investigational medicinal product.

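### SAP 12.2 bases its eye-symptom summaries on adverse events without naming the scripted form as a source, and gives neither duration nor percentage of days by symptom

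*SAP*

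**What the plan says.** **Endpoints.** Protocol section 3.2 (Table 6) lists "Frequency of participants with any new (vs. screening) eye symptom in one or both eyes" from Day 1 through Day 15. It also lists the mean and distribution of the duration of each symptom, and of the percentage of days with any symptom and with each symptom. Protocol Tables 2 and 9 and SAP Tables 2 and 4 carry the same endpoints; Protocol Table 9 and SAP Table 4 put duration in hours.

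**Who counts.** Protocol 8.3.7 states: "Participants with any eye symptom will contribute to secondary safety end-points". It attaches no AE condition to that sentence. The sentence before it, on the primary safety endpoint, does refer to eye-symptom AEs that are severe or serious.

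**When a symptom becomes an AE.** Also in Protocol 8.3.7: "Any eye symptom and/or abnormal visual acuity / color vision test outcome considered clinically meaningful by the investigator must be recorded as AE". Protocol 10.2.1 lists eye symptoms among the safety assessments that are AEs if considered clinically significant.

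**Collection.** The Appendix 5 form (Protocol 10.5.2) is completed on Days 1, 4, 7, 10, 14, 15, 28 and 42. For each symptom it records which eye, the start date and time, the length in hours and minutes, a medical term, seriousness and intensity.

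**Analysis.** SAP 12.2 says that the analysis of "eye symptom-related AEs for all eye symptoms, severe eye symptoms, and serious eye symptoms will be based on new events" after screening. Duration is "Average duration, expressed in hours, of eye symptom-related AEs in one or both eyes", averaged over a participant's events. For days: "Any day that a participant reported an eye symptom-related AE in one or both eyes after screening will be counted". SAP section 8 declares no change from the protocol's planned analyses.

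**The concern.** The protocol keeps two things apart: a symptom elicited by a standardized script, and an AE that depends on an investigator's judgement. The secondary endpoints are written on the first and SAP 12.2 is written on the second. If some scripted symptoms are not recorded as AEs, participants who had them count as symptom-free. Separately, two endpoints that the SAP itself lists have no matching summary in its methods section.

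Eye symptoms are among the most common events in the healthy-volunteer trial and appeared to follow peak concentration, and this is why the BID and TID regimens were included (Protocol 2.3). How often each symptom occurs, how long it lasts and on what share of days are what a reader would use to judge whether splitting the daily dose helps. A plan that pools symptoms, or leaves the data source to the programmer, weakens that description.

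**Working it through.** **1. Endpoint against planned output.**

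| Endpoint (SAP Tables 2 and 4) | What SAP 12.2 produces | Gap |
|---|---|---|
| Participants with any new symptom | Participants with eye-symptom AEs: by number of events, by preferred term, by visit | Restricted to AEs |
| Duration of each symptom | One average per participant over all eye AEs, shown for all, severe and serious | No result by symptom |
| Percentage of days with any and with each symptom, Days 1-15 | Number of days after screening, in bands up to 16 or more | Not a percentage, not by symptom, not confined to Days 1-15 |

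**2. Numerator and denominator by visit.** The by-visit denominator is participants with an eye symptom assessment. The numerator is participants with an eye-symptom AE. A participant who reports a symptom on the form that is not entered as an AE is in the denominator and counts as having none. By contrast, SAP 12.3 and 12.4 analyse the visual acuity and color vision results directly, with no AE step.

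**3. Pooled duration.** Take two of the SAP's own cut points as an example: one symptom of 1 hour and another of 5 hours in the same participant. The average is (1 + 5) / 2 = 3 hours, in the band above 1 and up to 3 hours. The two symptoms belong in the bands of up to 1 hour and of above 3 and up to 5 hours. The reported band describes neither. This holds even if every scripted symptom is an AE.

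**4. Days.** The endpoint window has 15 days, so 16 days would be 16/15 = 107% of it. The top category can be filled only by days outside the window.

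**5. Size.** The plan's only safety calculation is the chance of seeing at least one event (SAP 6.2), 1 - (1 - p)^n. It reproduces:

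- n = 15, p = 10%: 79.4% (stated 80%)
- n = 15, p = 15%: 91.3% (stated 90%)
- n = 15, p = 5%: 53.7% (stated 54%)
- n = 75, p = 3%: 89.8% (stated 90%)

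The documents give no share of scripted symptoms that becomes an AE. As an assumption only, let 20% of a group of 15 have a new symptom (3 expected) and let a fraction c of them have it recorded as an AE:

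| c | AE-based rate (20% x c) | Chance of at least one in 15 |
|---|---|---|
| 100% | 20% | 96.5% |
| 75% | 15% | 91.3% |
| 50% | 10% | 79.4% |
| 25% | 5% | 53.7% |

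At full recording the two counts agree. The table shows how the result depends on c; it does not estimate c.

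**The case against.** The best defence is that SAP 12.2 means the scripted data and merely labels them AEs. It uses hour bands, refers to one or both eyes, follows the eye-check days and uses the eye-assessment denominator. It tabulates preferred term, severity and seriousness, all of which the Appendix 5 form captures. The protocol blurs the line too: section 9.4.2.2 speaks of eye symptoms alongside other adverse events, the general AE definition in 10.2.1 covers any unfavorable symptom, and the clinical-meaning condition in 8.3.7 could be read as applying only to test results. This makes the source ambiguous, and it stands as a reason not to say that scripted symptoms are certainly excluded. It does not settle the matter: 10.2.1 does put eye symptoms under the clinical-significance condition, and a programmer following the SAP's words would use the AE data. Nor does it touch the missing by-symptom results.

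A reader might infer more than the documents support:

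- *That the any-new-symptom endpoint is absent.* It is not. An all-grade AE version with 95% confidence intervals is planned, with tables by term and by visit.
- *That AE records cannot resolve hours.* Protocol 10.2.6.1 says "The onset and resolution dates of an AE and action taken in response to the AE will be documented", but it does not say that times are not collected, and the AE form is not in the documents.
- *That mild, transient symptoms will be filtered out.* Protocol 2.3 reports such eye symptoms as treatment-emergent AEs in the earlier trial, so they were recorded there, and 8.3.7 asks for special attention to them.
- *That the script would escape open-label bias.* Participants and site staff know the treatment (Protocol 6.3.2), and the assessor assigns term, grade and seriousness on the form.

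SAP 9.1 lists all measured variables and tabulates them if appropriate, and 12.2 allows an optional exploratory analysis of eye symptoms. Both help, but neither commits to the endpoint tables.

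**Conclusion.** The point holds in two parts. First, as written, SAP 12.2 gives an AE-restricted and possibly narrower version of the any-new-symptom endpoint. It equals the protocol's endpoint only if every scripted symptom is recorded as an AE, and SAP section 8 does not declare the restriction. Second, and whatever the source, SAP 12.2 does not produce duration by symptom or percentage of days with any and with each symptom for Days 1-15. The second part rests on the text alone and needs no assumption.

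The size of the first part cannot be derived from the documents. Any stated gap in percentage points between regimens would rest wholly on assumed recording rates, and these summaries are descriptive, with no formal comparison to distort.

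**What to change.** In SAP 12.2:

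- Name the Appendix 5 eye symptom form as the source for the secondary eye-symptom endpoints. Define a case as any symptom in either eye that was not present at screening, whether or not it was recorded as an AE.
- Summarize frequency, duration and percentage of days by symptom for Days 1-15, with percentage of days also for any symptom. Take duration from the form's hours and minutes. State the denominator for percentage of days, and a rule for symptoms still ongoing at a check, since the form asks for length only once a symptom has ended.
- Keep the eye-symptom AE tables as separate AE summaries.
- If an AE restriction is intended, declare it in SAP section 8.

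The cost is SAP wording and a few more tables. No new data are needed, because the form is already completed at every eye check. The downside is that symptom rates may look higher than AE rates, so the two sets of tables need clear titles.

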2.3. Benefit/Risk Assessment

In this trial patients with untreated, drug-sensitive pulmonary TB will receive for 14 days either the test drug TBA-7371 in 1 of 5 regimens (from 100 mg QD to 400 mg QD) or commercial HRZE fixed combination (Rifafour® e-275) as control drug, dosed as recommended in the package insert.¹

HRZE is a first line treatment for drug sensitive TB with a well-established, generally favorable, yet not straightforward, benefit-risk profile. The most common AEs associated with HRZE are peripheral neuropathy, optic neuritis, hepatitis, and gastro-intestinal AEs (see Package Insert¹ and 2018 Safety Update² enclosed in study specific manual(s)).

TBA-7371 was tested in adult healthy volunteers in 1 clinical trial (TBA7371-001), composed of three parts: a single ascending dose (SAD) part where single doses from 100 to 800 mg were

tested, a multiple ascending dose (MAD) part where 100, 200 and 400 mg QD were taken for 14 days and a drug-drug interaction (DDI) part. The most common treatment-emergent adverse events (TEAEs) were increase in heart rate associated with decrease in blood pressure and eye symptoms (blurred vision, photophobia, altered color vision, increased lacrimation). The frequency of such events was dose related, starting at doses above 100 mg /day. Most were mild and transient. In particular, vision-related AEs were of short duration, resolved before the next dose and were not persistent changes. Furthermore, tachyphylaxis to changes in heart rate and blood pressure appeared to occur in the MAD part of the trial.

The eye symptoms appeared to be associated with C_{max} . It is therefore possible that the tolerability profile could improve with fractionation of the daily dose. This justifies the inclusion of the BID and TID dosing regimens in this trial.

There is no information on the efficacy of TBA-7371 in humans. PK/PD modelling from animal experiments, supplemented with additional PK data from healthy human subjects, suggests that bactericidal effect could be present at 100 mg/day and then increase with dose.

More information on TBA-7371 is provided in the Investigator Brochure.

The overall risks associated with TBA-7371 at or below 400 mg QD are considered low and are mitigated by the following design features of the present protocol:

- throughout the 14-day Treatment Phase eye symptoms, visual acuity and color vision, ECG will be assessed/recorded every 3-4 days, vital signs daily;

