6.4 Safety Measures

Table 4. Safety Endpoint

	Endpoint
Primary safety	Frequency of study participants who experienced one or more severe (\geq grade 3) and/or serious AEs from Day 1 through Day 15.
Secondary safety	
Adverse events from Day 1 through Day 15:
 
 • Frequency from Day 1 through Day 15 of participants with AEs and frequency of AEs: overall, by system organ class and preferred term; by seriousness, severity, expectedness and relatedness to study drug. 
Eye symptoms from Day 1 through Day 15:

Table 4. Safety Endpoint

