	
Frequency of participants with any new (vs. Screening) eye symptom in one or both eyes.Mean and frequency distribution of duration (hours) of each eye symptom.Mean and frequency distribution of percentage of days with any eye symptom and each of the eye symptoms.Mean/median change in visual acuity score from Screening to lowest score during Days 1-15.Frequency of participants with any new color vision abnormalities (tritan, protan, deutan) in one or both eyes and degree of severity (mild, moderate, severe). 
Heart rate (HR) and blood pressure (BP) from Day 1 through Day 15:
 
Mean and frequency distribution of changes in HR, SBP and DBP as measured by the following 2 (BP) or 3 (HR) methods:
Manual HR, SBP and DBP from vital signs, after at least 10 minutes in supine position (“manual, supine”);Manual HR, SBP and DBP from vital signs, after 2 (± 0.5) minutes in standing position (“manual, 2-min standing”);HR from ECG, supine position (“ECG, supine”)Frequency of participants with $\geq 25\%$ increase in HR, decrease in SBP, decrease in DBP vs. baseline as measured with any of the methods described above.Mean and frequency distribution of percentage of days with $\geq 25\%$ increase in HR, decrease in SBP, decrease in DBP vs. baseline.Mean/median change from screening through day 15 in RR, PR, QRS, QT, QTcF values from baseline ECG. 
Tachyphylaxis over the 14-day treatment period for HR, SBP, DBP and eye symptoms:
 
Mean change in HR, SBP and DBP from Baseline (Day 1, pre-dose) to Days 4, 7, 10, 14, and 15 for each of the 2 BP and 3 HR measurement methods described above.Change in frequency of participants with eye symptoms (all, severe, serious) and change in worst visual acuity score and frequency of color vision changes from Day 1 to Days 4, 7, 10, 14 and 15. 
Cardiovascular and/or ophthalmic AEs persistence or recurrence up to 4 weeks after discontinuation of treatment with TBA-7371:
 
Mean change in HR, SBP and DBP from Baseline (Day 1, pre-dose) to Days 28 and 42 and from Day 14 to Days 28 and 42 for each of the following measurement methods:
--	---

Table 4. Safety Endpoint

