12.5.2 Daily Vital Signs Results

Daily values of vital signs (HR, SBP, and DBP) measured while in supine and while in standing at baseline (Day 1 predose), Days 2 (predose), 3, 4 (predose), 5, 6, 7 (predose), 8, 9, 10 (predose), 11, 12, 13, 14 (predose), 15, 28, and 42 and changes from baseline will be summarized by treatment group using descriptive statistics. Line plots of mean of daily HR, SBP, and DBP measured while in supine and while in standing by treatment group will be provided.

Potentially clinically important criteria for changes from baseline in HR, SBP, and DBP while measured in supine and while in standing are defined as follows:

- $\geq 25\%$ increase in supine HR

- $\geq 25\%$ increase in standing HR
- $\geq 25\%$ decrease in supine SBP
- $\geq 25\%$ decrease in standing SBP
- $\geq 25\%$ decrease in supine DBP
- $\geq 25\%$ decrease in standing DBP

For each of the criteria, the frequency and proportion (expressed in percent) of participants who met the criterion at each time point will be provided by treatment group. For the by-time point summary, the denominator for the proportion is the number of participants in the treatment group with non-missing values at baseline and the given post-baseline time point.

For each of the criteria, any day that a participant whose vital signs results met the criterion will be counted toward the number of days with the criterion met in the study for that individual. Number of days with the criterion met will be summarized by treatment group using descriptive statistics.

Additionally, categorical number of days with the criterion met will be summarized by treatment group as follows:

- 1-3 days
- 4-6 days
- 7-9 days
- 10-12 days
- 13-15 days
- ≥ 16 days

The summary will include the frequency and proportion (expressed in percent) of participants for each category. For computing proportions, the denominator will be the number of participants in the treatment group who met the respective criterion.

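### SAP 12.2 counts raw eye-symptom days over the whole study, so the stated endpoint (percentage of days within Days 1–15) is not produced; SAP 12.5.2 makes the same substitution for heart rate and blood pressure

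*SAP*

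**What the plan says.** **Endpoint.** SAP 6.4 (Table 4) lists, under the heading "Eye symptoms from Day 1 through Day 15", the item "Mean and frequency distribution of percentage of days with any eye symptom and each of the eye symptoms". SAP Table 2 and Protocol Tables 2 and 6 give the same endpoint and window. Protocol Table 9 repeats the percentage without restating the window, and commits to summarising it by treatment group.

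**Analysis.** In SAP 12.2, each day with a report of "an eye symptom-related AE in one or both eyes after screening will be counted toward the number of days of having eye symptoms". The count covers a participant's whole time on study; no end day is named. The number of days is then summarised for all, severe and serious symptoms. A categorical table runs in three-day bands from 1–3 up to 13–15, with a last band of 16 or more days. For that table, "the denominator will be the number of participants with eye symptom-related AEs in the treatment group".

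**Vital signs.** The endpoint tables and Protocol 9.4.2.2 also promise the percentage of days with a change of at least 25% from baseline in heart rate or blood pressure. In SAP 12.5.2, each day on which a criterion is met "will be counted toward the number of days with the criterion met in the study for that individual", with the same bands.

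SAP section 8 declares no change from the protocol's planned analyses.

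**The concern.** Three features of the endpoint are lost between its definition and its analysis: the percentage, the Day 15 limit and the breakdown by individual symptom. A programmer who follows SAP 12.2 exactly will not produce the endpoint that the SAP itself lists.

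The open window matters because all participants move to standard TB treatment on Day 15. The documents do not give the composition of that treatment. However, Protocol 2.3 calls HRZE first-line for drug-sensitive disease and says of it: "The most common AEs associated with HRZE are peripheral neuropathy, optic neuritis, hepatitis, and gastro-intestinal AEs". Symptom days in follow-up would be counted under the randomised regimen although the participant is no longer taking it.

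Eye symptoms are among the main known safety findings for TBA-7371. According to Protocol 2.3, their apparent link with peak concentration is why the divided-dose regimens are included. A measure of symptom days on study drug bears directly on that comparison, and on the safety judgement that forms part of the study's success statement.

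**Working it through.** The plan gives no figure for this endpoint to reproduce. The check is a comparison of text, followed by day-count arithmetic.

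**1. Endpoint against analysis**

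| Feature | Endpoint tables | SAP 12.2 |
|---|---|---|
| Measure | Percentage of days | Number of days |
| Window | Days 1–15 | After screening, no end day |
| Symptoms | Any, and each | All, severe, serious |
| Day denominator | Implied by a percentage, not defined | None |
| Categorical table | Not restricted | Participants with events only |

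**2. Days that can be counted.** Protocol 8.4.1 collects adverse events to the Day 42 visit, or to the Early Withdrawal Visit.
- Day 1 to Day 42: 42 days; outside Days 1–15: 42 − 15 = 27; 27/42 = 64%.
- With the +3-day visit window: 45 days; 45 − 15 = 30; 30/45 = 67%.

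**3. The top band.** At most 15 days fit in the endpoint window. The band of 16 or more can be reached only by counting follow-up days.

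**4. Effect of the open window (illustrative completers)**
- 0 symptomatic days in Days 1–15 and 16 in follow-up: the SAP count is 16 (top band); the endpoint value is 0/15 = 0%.
- 3 in Days 1–15 and 13 in follow-up: the SAP count is 3 + 13 = 16 (top band); the endpoint value is 3/15 = 20%.

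**5. Effect of the denominator (illustrative)**

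| Participant | SAP band | Divided by days observed | Divided by fixed 15 |
|---|---|---|---|
| Withdrawn after Day 4, 3 symptomatic days | 1–3 | 3/4 = 75% | 3/15 = 20% |
| Completer, 3 symptomatic days | 1–3 | 3/15 = 20% | 20% |
| Withdrawn on Day 6, 6 symptomatic days | 4–6 | 6/6 = 100% | 6/15 = 40% |
| Completer, 6 symptomatic days | 4–6 | 6/15 = 40% | 40% |

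A percentage separates early withdrawals from completers only if its denominator is days observed. Neither document defines it.

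**6. Vital signs.** SAP 12.5.2 lists Day 1 predose as baseline, then Days 2–15, 28 and 42. That gives 14 post-baseline days in the window plus 2 in follow-up, 16 in all. Follow-up can add at most two scheduled days, and the top band is reached only if the criterion is met on all 16.

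**7. Alternative reading.** If only days of scheduled eye assessment count (Days 1, 4, 7, 10, 14, 15, 28 and 42), there are 8, and the top band cannot be reached on scheduled visits. The top band therefore fits the calendar-day reading better. On either reading, SAP 12.2 contains no percentage.

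**The case against.** Much of the eye-symptom output is already limited to the right period. SAP 12.2 tabulates participants with 1, 2 or at least 3 eye events during Days 1–15, with confidence intervals on the full Safety population, and shows Days 1–15 combined apart from Days 28–42 combined. The primary safety and adverse-event overview tables also stop at Day 15. This stands, but those tables count participants, not days, so they do not supply the endpoint.

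The top band may be a reused template, since the same list appears in SAP 12.2, 12.5.2 and 12.5.3. That weakens it as evidence of intent. The count still has no end day, whereas the participant counts in the same section name one. A distribution among affected participants is also a legitimate complement to incidence; it is just not the endpoint.

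A reader might infer more than the documents support:
- **That follow-up days count against TBA-7371 in particular.** All arms, including HRZE, switch to standard treatment and all gain follow-up days. The net direction between arms cannot be determined.
- **That the SAP departs from the endpoint by making early withdrawals look safer.** This holds only if the undefined denominator is days observed. With a fixed 15, the stated endpoint has the same limitation. Protocol 7.2 expects withdrawals to be uncommon, and events leading to discontinuation are tabulated separately.
- **That long follow-up symptoms will dominate the count.** A symptom lasting from Day 20 to Day 42 gives 23 days, 23/15 = 1.5 times the window maximum. Protocol 2.3 reports that vision-related events in the first trial were short and resolved before the next dose.
- **That SAP 12.5.2 is affected to the same extent.** At most two scheduled follow-up days enter there.

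**Conclusion.** The mismatch is real and is wrong as written, not merely under-specified. SAP 12.2 does not produce the percentage-of-days endpoint, for any symptom or for each symptom, and it combines days on study drug with follow-up days. SAP 12.5.2 also omits its stated percentage, with a much smaller follow-up contribution.

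Up to 27 of 42 countable days (64%) lie outside the window for eye symptoms. This rests on reading the count as calendar days to Day 42; the missing percentage does not depend on that reading. The participant examples are illustrative. The size of any bias cannot be computed, because the documents give no dropout rate and no eye-symptom rate. These are descriptive secondary analyses with no formal test, so the point should be corrected but does not touch the primary efficacy inference.

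**What to change.** In SAP 12.2 and 12.5.2:
- Count days within Days 1–15 only.
- Divide by days observed in that window, and state this denominator explicitly. A fixed 15 would understate symptom burden in early withdrawals. For vital signs, use days in the window with a post-baseline measurement.
- Summarise the percentage for all treated participants, entering zero for those without events.
- Report it for any eye symptom and for each eye symptom, and for each heart-rate and blood-pressure criterion.
- Replace the day bands, including 16 or more, with percentage bands.
- Report follow-up days separately under the persistence objective.

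The severe and serious breakdowns, and the table among affected participants, can stay as supplements. If the sponsor prefers raw days, SAP section 8 should declare the change.

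The cost is SAP wording and a revised derivation. The eye-symptom form in Protocol Appendix 5 already records start date, start time and duration, so no new data are needed.
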